#### 7.5.1.3. Patient Global Impression of Change

The PGIC is a participants' self-reporting measure that reflects their belief about the efficacy of treatment. The PGIC is a 7-point scale depicting a participant's rating of overall improvement of CHE and will be captured during postbaseline visits (Hurst and Bolton 2004).

The participant will be asked to select 1 response from the response options that best describe the overall change in their CHE since they started study treatment: 1) very much improved, 2) much improved, 3) minimally improved, 4) no change, 5) minimally worse, 6) much worse, and 7) very much worse. Missing values will not be imputed.

## 7.5.1.4. Dermatology Life Quality Index

The DLQI is a simple, 10-question validated questionnaire to measure how much the skin problem has affected the participant over the previous 7 days in all the scheduled visits in both DBVC and OLE period (Finlay and Khan 1994).

The questionnaire is analyzed under 6 subscales as follows:

- Symptoms and feelings (Questions 1 and 2)
- Daily activities (Questions 3 and 4)
- Leisure (Questions 5 and 6)
- Work and school (Question 7)
- Personal relations (Questions 8 and 9)
- Treatment (Question 10)

The scoring of each question is as follows: Very much = 3; A lot = 2; A little = 1; Not at all = 0; Not relevant = 0; Question 7, "Prevented work or studying" Yes = 3.

The following imputation will be applied for incorrectly completed questionnaires:

- If 1 question is left unanswered, this is scored 0 and the scores are summed and expressed as usual out of a maximum of 30.
- If 2 or more questions are left unanswered, the questionnaire is not scored.
- If question 7 is answered "yes," this is scored 3. If Question 7 is answered "no," but then either "a lot" or "a little" is ticked, this is then scored 2 or 1. If 'Not relevant" is ticked, the score for Question 7 is 0. If it is answered "no," but the second half is left incomplete, the score will remain 0.
- For the 6 subscales, if the answer to one question in a subscale is missing, that subscale should not be scored.

The DLQI is calculated by summing the score of each question resulting in a maximum of 30 and a minimum of 0. The higher the score, the more quality of life is impaired.

#### 7.5.1.5. EQ-5D-5L

Participants will complete the EQ-5D-5L questionnaire at the scheduled visits in DBVC and OLE periods. The EQ-5D-5L questionnaire is a standardized, validated instrument for use as a measure of health outcome (Herdman et al 2011). The EQ-5D-5L questionnaire consists of the following 2 sections: the EQ-5D descriptive system and the EQ VAS.

The descriptive system comprises 5 dimensions: mobility, self-care, usual activities, pain/discomfort, and anxiety/depression. Each dimension has 5 levels: Level 1 = no problems, Level 2 = slight problems, Level 3 = moderate problems, Level 4 = severe problems, and Level 5 = extreme problems.

The EQ VAS records the participant's self-rated health on a vertical VAS (0-100), where the endpoints are labeled "the best health you can imagine" (100 score) and "the worst health you can imagine" (0 score).

Missing values will not be imputed. The categorical outcomes for the 5 dimensions (mobility, self-care, usual activity, pain/discomfort, and anxiety/depression) will be summarized. The change from baseline in EQ-5D VAS score will be analyzed.

## 7.5.1.6. Quality of Life in Hand Eczema Questionnaire

Participants will complete the QOLHEQ at the scheduled visits in DBVC and OLE periods. The QOLHEQ is a validated disease-specific instrument to assess disease-specific health-related quality of life in participants suffering from CHE over the past 7 days (Ofenloch et al 2014). It consists of 30 items that are summarized according to impairments for 4 subscales: 1) symptoms, 2) emotions, 3) limitations in functioning, and 4) treatment and prevention. Each item is scored in a scale of never, rarely, sometimes, often, all the time. The overall score is calculated by summing up all items.

Table 6 shows the scoring for each QOLHEQ item with the item number corresponds with the position of the item in the QOLHEQ.

**Table 6:** Scoring of Quality of Life in Hand Eczema Questionnaire

Item Number	Scoring of the item (never-rarely-sometimes-often-all the time)
Symptoms	
1	0-1-2-3-4
6	0-1-2-3-4
9	0-1-2-3-4
11	0-1-2-3-4
20	0-1-2-3-4
23	0-1-2-3-4
28ª	0-1-1-2-3
Emotions	
5	0-1-2-3-4
8	0-1-2-3-4
10 a	0-1-1-2-3
16	0-1-2-3-4
19	0-1-2-3-4
21	0-1-2-3-4
27	0-1-2-3-4
30	0-1-2-3-4

Table 6: Scoring of Quality of Life in Hand Eczema Questionnaire (Continued)

Item Number	Scoring of the item (never-rarely-sometimes-often-all the time)	
Limitations in function	ing	
2	0-1-2-3-4	
3	0-1-2-3-4	
12	0-1-2-3-4	
14	0-1-2-3-4	
15	0-1-2-3-4	
17	0-1-2-3-4	
25	0-1-2-3-4	
29	0-1-2-3-4	
Treatment and prevent	ion	
4ª	0-1-1-2-3	
7	0-1-2-3-4	
13	0-1-2-3-4	
18	0-1-2-3-4	
22	0-1-2-3-4	
24	0-1-2-3-4	
26	0-1-2-3-4	

<sup>a In general, all items are scored 0-4 and only 3 items differ in their scoring structure.

The following imputation will be applied for incorrectly completed questionnaires (QOLHEQ 2024):

- If 1 question is left unanswered, this is scored as 0 and the subscale score is calculated by summing up all items.
- For the 4 subscales, if the answer to more than 1 question in a subscale is missing, that subscale should not be scored.
- If 4 or more questions are left unanswered, the overall score is set to missing and should not be scored.

# 7.5.1.7. Work Productivity and Activity Impairment Questionnaire Specific Health Problem v2.0 in Chronic Hand Eczema

Participants will complete the WPAI-ChHD questionnaire at the scheduled visits in DBVC and OLE periods. The Work Productivity and Activity Impairment Questionnaire is a patient-reported quantitative assessment of the amount of absenteeism, presentism, and daily activity impairment attributable to a specific health problem (Reilly et al 1993). The WPAI-ChHD is a 6-item questionnaire used to assess the impact of chronic hand dermatitis (ChHD, the same as CHE in this context) on job performance and productivity in the last 7 days.

Work Productivity and Activity Impairment outcomes are expressed as impairment percentages, with higher numbers indicating greater impairment and less productivity, ie, worse outcomes, as follows:

## Questions:

- 1 = currently employed
- 2 = hours missed due to CHE
- 3 = hours missed other reasons
- 4 = hours actually worked
- 5 = degree CHE affected productivity while working
- 6 = degree CHE affected regular activities

#### Scores:

Multiply below scores by 100 to express in percentages (%).

- Percent work time missed due to CHE: Q2 / (Q2 + Q4)
- Percent impairment while working due to CHE: Q5 / 10
- Percent overall work impairment due to CHE:  $[Q2/(Q2+Q4)] + (\{1-[Q2/(Q2+Q4)]\} \times [Q5/10])$
- Percent activity impairment due to CHE: Q6 / 10

These impairment percentages will be summarized by visit and by treatment. Missing values will not be imputed.

#### 7.5.2. Secondary Efficacy Analysis

All secondary efficacy analyses will be conducted based on the ITT population during the treatment period (DBVC and OLE periods).

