10.4.3. Secondary Analysis

All other secondary and exploratory efficacy variables will be summarized using descriptive statistics. For categorical measurements, summary statistics will include sample size, frequency, and percentages. For continuous measurements, summary statistics will include sample size, mean, median, standard deviation, standard error of the mean, minimum, and maximum. For the

time to achieve change from baseline in CHE-related Itch NRS score \geq 4 and in CHE-related Skin Pain NRS score \geq 2, a log-rank test stratified by randomization stratification factors will be used for comparisons between treatment groups. The hazard ratio and its 95% CI will be estimated based on the stratified Cox regression model using Efron's method accounting for ties. Kaplan-Meier curves will be presented by treatment groups. The number of participants, number of events, and number of censoring will be summarized by treatment groups. The Kaplan-Meier estimate of median time will be presented with its 95% CI. The 95% CI will be calculated using the method by Brookmeyer and Crowley (1982).

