#### 3. STUDY DESIGN

[figure not shown]
This is a Phase 2, randomized, double-blind, vehicle-controlled, 16-week study followed by a 16-week open-label treatment extension period. Approximately 180 participants with moderate to severe CHE with no history of (within the past 5 years) or current AD will be randomized 1:1 to either ruxolitinib 1.5% cream or vehicle cream. Participants will apply either ruxolitinib 1.5% cream or vehicle cream (both BID) to CHE lesions on the hands and wrists (if applicable) for 16 weeks. All areas identified at baseline should continue to be treated through the end of the DBVC period (Week 16) unless the participant meets criteria for stopping study drug.

At Week 16, participants with no safety concerns will enter the 16-week OLE period, during which all participants will receive open-label ruxolitinib 1.5% cream. Affected areas will be treated as needed until they clear during the OLE period.

Participants, investigators, and the sponsor will be blinded to each participant's treatment assignment during the DBVC period. During the OLE period, participants and investigators will remain blinded to the treatment assignment during the DBVC period until after all participants have completed treatment or discontinued and completed the safety follow up period.

Figure 1 presents the study design schema.

Figure 1: Study Design Schema

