#### 4.1.3. Baseline Value

Baseline is the last nonmissing measurement obtained before or on the day of first application of ruxolitinib cream or vehicle cream for DBVC period.

For randomized participants not treated with any study drug, baseline is defined as the last nonmissing assessment before or on the day of randomization for all parameters.

For participants who continue in the OLE period, baseline for OLE is defined as follows:

- For efficacy evaluation, baseline is the last nonmissing measurement obtained before or on the day of first application of study treatment in DBVC period.
- For safety evaluation, for participants who cross over from vehicle group to ruxolitinib cream, the baseline is the last nonmissing measurement obtained before or on the day of first application of ruxolitinib cream in the OLE period; for participants on ruxolitinib cream in both periods, baseline is the last nonmissing measurement obtained before or on the day of first application of study treatment in DBVC period.

When scheduled assessments and unscheduled assessments occur on the same day and time of the assessment or time of first application is not available, use the following convention to determine baseline:

- If both a scheduled and an unscheduled visit are available on the day of the first application and the time is missing, use the scheduled assessment as baseline.
- If all scheduled assessments are missing on the day of the first application and an unscheduled assessment is available, use the unscheduled assessment as baseline.

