## **5.2.** Treatment Groups

This is a randomized, DBVC study followed by an OLE period. Data will be summarized based on treatment regimen that was assigned (ITT) or that the participant actually applied (safety).

For analyses in the ITT population and safety population, the treatment groups will be ruxolitinib 1.5% cream BID and vehicle cream BID.

For analyses in the open-label evaluable population, the treatment groups will be ruxolitinib 1.5% cream BID and vehicle cream BID to ruxolitinib 1.5% cream BID.

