## 5.3. Analysis Populations

#### **5.3.1.** Intent-to-Treat Population

All participants who are randomized to the study will constitute the ITT population. Treatment groups for this population will be defined according to the treatment assignment at the time of randomization regardless of the actual study treatment the participant might apply during their participation in the study.

The ITT population will be used for the summary of demographics, baseline characteristics, participant disposition, and analyses of all efficacy data.

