## 7.5.2.3. Time-To-Event Efficacy Endpoints

For the time to achieve CHE-related Itch NRS score improvement of at least 4 points and time to achieve CHE-related Skin Pain NRS score improvement of at least 2 points, a log-rank test stratified by randomization stratification factors will be used for between treatment group comparisons. The hazard ratio and its 95% CI will be estimated based on the stratified Cox regression model using Efron's method accounting for ties. Kaplan-Meier curves will be presented by treatment groups. The number of participants, number of events and number of

censoring will be summarized by treatment groups. The Kaplan-Meier estimate of median time will be presented with its 95% CI. The 95% CI will be calculated using the method by Brookmeyer and Crowley (1982).

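### SAP 7.5.2 carries the itch and skin-pain time-to-event comparisons into the open-label period, and 7.5.2.3 gives no horizon or censoring rule to stop them at Week 16

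*SAP*

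**What the plan says.** - **Period.** SAP 7.5.2, the parent of the time-to-event section, reads: "All secondary efficacy analyses will be conducted based on the ITT population during the treatment period (DBVC and OLE periods".
- **Method.** SAP 7.5.2.3 covers time to a 4-point itch improvement and time to a 2-point skin-pain improvement. It says that "a log-rank test stratified by randomization stratification factors will be used for between treatment group comparisons", adds a stratified Cox hazard ratio and Kaplan-Meier curves, and says "The Kaplan-Meier estimate of median time will be presented with its 95% CI". It promises a count of censored participants but never says when anyone is censored. Protocol 10.4.3 has the same test ("a log-rank test stratified by randomization stratification factors will be used for comparisons between treatment groups") and the same gap.
- **Groups.** SAP 5.2: "For analyses in the ITT population and safety population, the treatment groups will be ruxolitinib 1.5% cream BID and vehicle cream BID". SAP 5.3.1 keeps the randomized label "regardless of the actual study treatment the participant might apply during their participation in the study".
- **OLE treatment.** SAP 3 says of the OLE that "all participants will receive open-label ruxolitinib 1.5% cream".
- **OLE baseline and data.** SAP 4.1.3: "For efficacy evaluation, baseline is the last nonmissing measurement obtained before or on the day of first application of study treatment in DBVC period". SAP 7.4.1.1 and 7.5.1.2 run both diaries to Week 32 or early termination.
- **Displays (SAP Appendix A).** Tables 2.2.4 and 2.3.3 are titled for the treatment period. The matching Kaplan-Meier Figures 4.3.5.1 and 4.4.3 are titled for the DBVC period.

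**The concern.** Taken together, these rules leave nothing to stop the clock at Week 16. A participant randomized to vehicle who first responds in Week 20, after four weeks of ruxolitinib, counts as a vehicle response. A by-visit table does not have this problem, because Week 16 sits in its own row, apart from Weeks 24 and 32. A hazard ratio, a log-rank p-value and a median each pool all follow-up into one number, so the horizon decides what they estimate. Up to Week 16 they compare ruxolitinib with vehicle; beyond it they drift towards early versus delayed ruxolitinib.

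Two practical consequences follow. The table and the curve for the same endpoint could rest on different follow-up. And because SAP 10 unblinds the sponsor after the primary database lock, an unstated horizon could be settled with treatment codes known.

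**Working it through.** **1. Side by side.** Four places bear on the period of the time-to-event analysis.

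| Place | Period |
|---|---|
| SAP 7.5.2 (governing text) | DBVC and OLE |
| SAP 7.5.2.3 and Protocol 10.4.3 | none stated |
| Tables 2.2.4, 2.3.3 | treatment period |
| Figures 4.3.5.1, 4.4.3 | DBVC period |

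The SAP sets limits elsewhere: the next-period cut in 4.1.4 (last available value) and 9.2.1 (treatment-emergent events), and Week 16 for pain response in 7.5.2.2. None of these is applied to 7.5.2.3.

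**2. The plan's own figure.** No power or hazard ratio is stated for these endpoints. The nearest figure is ITCH4 at Week 16: 40% vs 18%, 90 per arm, chi-square, 2-sided 0.05.
- Null SE = √(2 × 0.29 × 0.71 / 90) = 0.0676.
- Alternative SE = √((0.24 + 0.1476) / 90) = 0.0656.
- z = (0.22 − 1.96 × 0.0676) / 0.0656 = 1.33, so power is 90.9% (stated 90%). The inputs reproduce.

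**3. Events at 40% vs 18%.** Assumptions: these rates are used as cumulative first response, hazards are constant, there is no dropout, everyone enters the OLE, and crossovers take the ruxolitinib hazard.
- Hazard ratio to Week 16 = ln(0.60)/ln(0.82) = 2.57.
- Events by Week 16: 90 × 0.40 + 90 × 0.18 = 36.0 + 16.2 = 52.2.
- Events in Weeks 17–32: ruxolitinib 54.0 × 0.40 = 21.6; vehicle starters 73.8 × 0.40 = 29.5. Total by Week 32: 103.3.
- Share of vehicle events that occur on ruxolitinib: 29.5 / (16.2 + 29.5) = 65%.
- After Week 16 the true hazard ratio is 1. Weighting the log hazard ratios by events: exp(ln 2.57 × 52.2/103.3) ≈ 1.61.
- Simulation (4,000 trials, unstratified) agrees: hazard ratio 2.61 falls to 1.58, power 91% falls to 65%, and the significance conclusion differs between the two horizons in 29% of trials.

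**4. Range over other assumptions (simulated, 90 per arm).**

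| First response by Week 16 | After crossover | HR, Week 16 → Week 32 |
|---|---|---|
| 95% vs 85% | constant hazard | about 1.6 → about 1.55 |
| 90% vs 70% | constant hazard | 1.94 → 1.77 |
| 70% vs 40% | late ruxolitinib hazard | 2.42 → 1.92 |
| 70% vs 40% | replays ruxolitinib curve | 2.41 → 1.37 |
| 40% vs 18% | constant hazard | 2.61 → 1.58 |
| 40% vs 18% | replays ruxolitinib curve | about 2.6–2.7 → about 1.0–1.1 |

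The last row takes the planning rates of Protocol Table 9 (30/35/40% vs 10/12/18% at Day 7, Week 4 and Week 16) as the shape of cumulative first response. With 15% dropout and 90% OLE entry it ends at 1.21.

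**5. Median.** At 70% vs 40% the vehicle curve has no median in the DBVC period, because fewer than half respond. Followed on at the constant ruxolitinib hazard, it reaches 50% after ln(0.60/0.50) / (−ln(0.30)/112) = 17 days of open-label treatment, Day 129. That would be printed as a vehicle median.

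**The case against.** The strongest reply is that a DBVC analysis was probably meant and simply not written down. Much of that stands.

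- The Kaplan-Meier figures are the only displays of these endpoints with a period-specific title, and both say DBVC.
- The treatment-period label proves little. Tables 2.1.2 and 2.2.2 carry it too, for nonresponder-imputation analyses that SAP 7.3.2 and 7.4.2 place in the DBVC period. A reader might infer from Tables 2.2.4 and 2.3.3 that the sponsor chose an open-label horizon; the titles do not support that.
- SAP 7.5.2 is a general scope sentence, and 7.5.2.2 departs from it with limits at Week 16 and Day 14.
- The appendix calls its lists guidelines, and the table shells are in a separate document not seen here.
- SAP 7.4.1.1 bases time to itch improvement on daily scores. Over 16 weeks of daily entries, first response may be far commoner than the visit-level rates in Table 9, and the effect is then small.

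These points weaken the claim about intent and the larger figures. They do not remove the defect. The one sentence that assigns a period to these analyses includes the OLE, 7.5.2.2 writes its exceptions out while 7.5.2.3 writes none, and a figure title in a list of guidelines cannot override the body text. A programmer who follows the SAP as written would include OLE events.

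**Conclusion.** The point holds as a fault in the governing text, with the table and figure mismatch as supporting evidence. Followed literally, SAP 7.5.2 makes the time-to-event comparison one of early versus delayed ruxolitinib, and the hazard ratio is pulled towards 1. The pull is negligible when most participants respond by Week 16 and large when few do. The documents give neither first-response rates nor post-crossover hazards, so the figures show direction and range and are not a forecast. The drop to 1.0–1.1 in particular needs both the Table 9 rates as first-response rates and a full replay of the early ruxolitinib curve.

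Two stronger conclusions might be inferred, and neither is supported.
- *The trial's main findings are at risk.* They are not. The primary and key secondary tests are separate, these tests lie outside the fixed sequence in SAP 3.2, and the bias usually runs against the drug, so a false efficacy claim is unlikely.
- *The cumulative safety tables have the same fault.* SAP 5.2 refers to treatment actually applied, 9.2.1 makes event windows period-specific for crossovers, and separate DBVC and OLE tables are planned.

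The point should be fixed, and it is a matter of wording.

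**What to change.** In SAP 7.5.2.3, as a stated exception to 7.5.2:

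1. Restrict the log-rank, Cox and Kaplan-Meier comparisons for itch and skin pain to the DBVC period.
2. Count events, and censor participants without one, using diary entries made before the first OLE application and no later than Week 16 or early termination. Exclude the evening entry on the day of that application: Protocol 6.1 has the visit-day application made in clinic, and Protocol 8.2.6.1 has the diary completed in the evening with 24-hour recall, so that entry follows open-label dosing. A rule of on or before that date would let it in.
3. State how discontinuation before Week 16 is handled. One option is to censor at the last DBVC entry, with a sensitivity analysis that keeps discontinued participants as non-events to Week 16. The latter is closer to the nonresponder rule that SAP 7.4.2 uses for ITCH4 at Weeks 4 and 16.
4. Retitle Tables 2.2.4 and 2.3.3 for the DBVC period, to match Figures 4.3.5.1 and 4.4.3.

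The cost is SAP wording, two table titles and some programming. No new data are needed and trial conduct does not change. The rule should be on record before the primary database lock.

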## 7.5.2.1. Continuous Efficacy Endpoints

By-visit summary statistics for the following continuous measurements, including change from baseline and percentage change from baseline will be presented:

- CHE-related Itch NRS score
- CHE-related Skin Pain NRS score
- HECSI score
- DLQI total score
- EQ-5D-5L VAS score
- QOLHEQ total score
- WPAI-ChHD scores

The summary statistics includes sample size, mean, median, standard deviation, minimum, maximum, 1st quartile, 3rd quartile, and 95% CI will be presented by visits.

For PGIC score, summary statistics will be presented by treatment group at each postbaseline visit.

#### 7.5.2.2. Categorical Efficacy Endpoints

For the following categorical parameters, summary statistics including sample size, frequency, and percentages will be presented by visits.

- Proportion of participants achieving an IGA-CHE-TS
- Proportion of participants achieving ≥ 2-point improvement in CHE-related Skin Pain NRS score up to Week 16 from baseline.
- Proportion of participants achieving ≥ 4-point improvement in CHE-related daily Itch NRS score from baseline to Day 14.

Statistical analysis for the ITCH4 response at Day 3 will be conducted using models similar to the key secondary endpoint of ITCH4 at Day 7, specified inSection 7.3.2.

For the following categorical endpoints, the number and percentage of participants will be summarized by treatment at each postbaseline visit:

- Proportion of participants in each category of EQ-5D-5L score
- Proportion of participants with each score on the PGIC

